**Figure 3.1:1 Trial design**

**Retrospective phase:** At least 4 Serum Creatinine measurements at minimum. However, it is desirable to have as many as available.

**Prospective phase:** 48 weeks duration. Site visits – Blood sample collection at baseline and every 12 weeks (i.e. Week 12, Week 24, Week 36, Week 48). Urine sample collection (for UACR determination) at baseline and Week 48. At home (using Mitra® Device) blood samples will be collected on a biweekly basis for the first 12 weeks and thereafter on a 4-weekly basis until Week 48. If site visit coincides, Mitra® device sample will be collected in combination with venous sample on site.

\* Screening period of up to 2 weeks between retrospective and prospective phases.

# Baseline visit is considered as Visit 2/Day 1 of prospective phase

An interim analysis can be considered at any time, based on recruitment/feasibility as outlined in section 4.10.1.4. Its purpose is to best utilize all available data collected up to these timepoints, if it is identified that enrolment is not sufficient to reach the recruitment goal by the currently targeted study end.

A schedule of assessments to be performed at each study visit can be found in the flow chart of the clinical trial protocol (CTP).

### 3.1.1.1 Study Termination

This study was terminated in July 2022, due to decision of the sponsor. All data available up to the termination will be used in any subsequent analyses and all analyses planned in this SAP (and the corresponding TLF shells) will be performed.

## 3.2 Endpoints

### 3.2.1 Primary Outcome Variables

The following variables will be used in the analysis of the primary outcome:

- eGFR measurements collected from the retrospective phase.
- eGFR measurements collected from the prospective phase.

### 3.2.3 Safety Variables

The following variables will be included in the analysis of safety:

- Adverse event (AE) assessments.
- Clinical laboratory evaluations.
- Physical examinations.
- Vital signs assessments (heart rate [beats/min], systolic blood pressure [mmHg], diastolic blood pressure [mmHg]).

## 4 STATISTICAL METHODS

### 4.1 Data Quality Assurance

All tables, figures and data listings to be included in the report will be independently checked for consistency, integrity and in accordance with standard [REDACTED] procedures.

### 4.2 General Presentation Considerations

For each patient, the date of baseline, i.e. Day 1 of the study, is defined as the earliest assessment taken across all domains/measurements on Visit 2 of the prospective phase. For individual domains, the latest measurement on or before Visit 2 will be used as the baseline measurement. 'End of Study' is defined as the last available post-baseline assessment. For the prospective phase, 'Study Day' will be calculated relative to the date of baseline such that Study Day = Assessment Date – Date of Baseline +1. For the retrospective phase, 'Study Day' will be calculated relative to the date of baseline such that Study Day = Assessment Date – Date of Baseline (note that the resulting study day will be negative for retrospective data).

Continuous data will be summarized in terms of the mean, standard deviation (SD), median, minimum, maximum and number of observations, unless otherwise stated. Continuous data that are expected to be skewed will be presented in terms of the maximum, upper quartile, median, lower quartile, minimum and number of observations. The minimum and maximum will be reported to the same number of decimal places as the raw data recorded in the database. The mean, SD, median, lower quartile and upper quartile will be reported to one more decimal place than the raw data recorded in the database. In general, the maximum number of decimal places reported shall be 4 for any summary statistic.

Categorical data will be summarized in terms of the number of patients providing data at the relevant time point (n), frequency counts and percentages. Any planned collapsing of categories will be detailed in the SAP text and the data displays.

Percentages will be presented to one decimal place. Percentages will not be presented for zero counts. The denominator for percentages will be further specified in this SAP. If sample sizes are small, the data displays will show the percentages, but any textual report will describe frequencies only.

P-values greater than or equal to 0.001, in general, will be presented to 3 decimal places. P-values less than 0.001 will be presented as "<0.001". Confidence intervals (CIs) will be presented to one more decimal place than the raw data.

### 4.3 Handling of Dropouts or Missing Data

In the primary analysis of all continuous endpoints, missing data will not be imputed. Further details of the handling of missing data for specific endpoints will be detailed in the relevant analysis section of this SAP.

### 4.4 Software

All report outputs will be produced using SAS® version 9.4 or a later version in a secure and validated environment.

### 4.5 Study Patients

#### 4.5.1 Disposition of Patients

Patients are considered to have entered the study if they successfully complete the screening and complete the baseline assessment.

Disposition summaries will be based on the enrolled set, and will be done by patient population (DKD/non-DKD patients) and overall. A summary of the number of patients enrolled, screened, who entered or did not enter the study, with reason why patient did not enter will be presented. A breakdown of the number of patients that did not meet each inclusion/exclusion criterion and were subsequently screen failures will also be presented. Additionally the percentage will be presented for the number who entered the study. The number and percentage of patients who completed the study, or prematurely discontinued the study will be presented along with each reason for discontinuation. Percentages will be based on the number of patients who entered the study.

A by-patient listing of disposition will also be presented for all enrolled patients, including patient identifier, site, country, patient population (DKD/non-DKD), age, sex, main informed consent date, whether patient entered study, reason patient did not enter study (if applicable) including any text entered in the eCRF under the category 'other', study status (completed/ongoing/discontinued), reason for study discontinuation (if applicable) and date of study completion or study discontinuation.

#### 4.5.2 Protocol Deviations

Major protocol deviations (PDs) are defined as those deviations from the protocol likely to have an impact on the patient's rights, safety, well-being, and/or validity of the data for analysis. Major PDs and any action to be taken regarding the exclusion of patients or affected data from specific analyses are defined in the project-specific Protocol Deviation Specification.

A summary of the number and percentage of patients with a major protocol deviation by type of deviation will be presented for all patients who entered the study, along with the number of patients with a major protocol deviation leading to exclusion from the Full Analysis Set (FAS) by deviation, with percentages based on the number of patients who entered the study.

A by-patient listing of major protocol deviations will also be presented, including the patient identifier, patient population, site, country, PD classification (e.g. 'Inc/Excl Criteria'), PD description, and indication if PD led to exclusion from the FAS for all patients who entered the study.

#### 4.6 Analysis Sets

The enrolled set includes all patients for whom main informed consent was obtained.

All analyses will be based on the FAS, which will consist of all patients entered into the 48-week prospective phase of the study who have at least one post-baseline assessment. Since this is a non-randomized study with no trial drug administration, there is no need for a separate Safety Analysis Set, and both safety and non-safety summaries will be done on the FAS.

Upon database release, protocol deviation and analysis set outputs will be produced and will be sent to Boehringer Ingelheim for review. An analysis set classification meeting will be arranged if applicable to discuss the outputs and to decide which patients and/or patient data will be excluded from certain analyses. Decisions made regarding the exclusion of patients and/or patient data from analyses will be made prior to the final analysis, and will be documented and approved by Boehringer Ingelheim.

A summary of the number and percentage of patients in each analysis set will be presented for the enrolled set, with denominators based on the number of patients who were enrolled. The number of patients not included in the FAS with the reason for exclusion will also be presented, with denominators based on the number of patients who were enrolled.

A by-patient listing of analysis set details will be presented for all enrolled patients, including the patient identifier, patient population, site, country and indication of inclusion/exclusion from each analysis set, and reason for exclusion (from FAS only). If patient data has been partially excluded from an analysis set, details of the data and visit that has been excluded will appear on this listing.

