3.3.2 Inclusion criteria

1. Signed and dated written informed consent in accordance with ICH-GCP and local legislation prior to admission to the trial.
2. Patients with available medical records for data abstraction to meet the objectives of the study.
3. Male or female patients aged ≥ 18 years at time of consent.
4. Body Mass Index (BMI) ≥ 18.5 and < 50 kg/m² at Visit 1.
5. Clinical diagnosis of CKD.
6. eGFR decline of at least 1ml/min/1.73m²/year based on historical data from (electronic) medical records.
7. eGFR (Chronic Kidney Disease Epidemiology Collaboration [CKD-EPI] formula) 20 – 90 ml/min/1.73m² at Visit 1 calculated from serum creatinine measured by a central laboratory.
8. Patients are expected to be on optimal and stable background treatment (according to local therapy guidelines).
9. At least 4 serum creatinine values in the retrospective phase:
 - The most recent creatinine value not more than 6 months prior to Visit 1 (Screening Visit).
 - The most recent and oldest serum creatinine values should be no less than 1 year apart and no greater than 5 years apart.
 - There should be no gap of creatinine values of 2 years or longer.

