This study will provide information on the availability, frequency and continuity of retrospective eGFR and Urine Albumin Creatinine Ratio/Protein Creatinine Ratio (UACR/PCR) data in patient medical records, as collected via routine clinical practice. The study will also compare eGFR slopes derived via retrospective serum creatinine values collected up to 5.5 years prior to visit 1 in routine clinical practice, with prospectively generated eGFR values and resulting slopes. [REDACTED]

The scope of this statistical analysis plan (SAP) is to describe the rules, conventions and statistical methods to be used in the presentation and analysis of data for clinical trial 1366-0026.

The analyses described in this SAP are based upon the following study documents:

- Clinical Trial Protocol, version 3.0 (25 Apr 2022)
- Electronic Case Report Form (eCRF), version 5.0 (02 June 2022)
- Electronic Laboratory Data Transfer Specifications, version 2.0 (15 December 2021)
- [REDACTED], version 2.0 (22 April 2022)

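### Summaries of routine eGFR record availability and continuity default to the FAS, a set selected on those same record features, so they are conditional on eligibility and should also be shown on the enrolled set

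*SAP*

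**What the plan says.** The aim is in SAP 1, and in the same terms in Protocol 1.3: "This study will provide information on the availability, frequency and continuity of retrospective eGFR" and UACR/PCR data in medical records from routine practice. Both documents link it to regulatory advice to evaluate retrospective slopes further, including how they can be built from patient records.

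SAP 4.6 defines the analysis population: "All analyses will be based on the FAS, which will consist of all patients entered into the 48-week prospective phase" who also have at least one post-baseline assessment. The same section defines a wider enrolled set, made up of everyone who gave main informed consent.

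Protocol 3.1 makes the requisite historical eGFR data a condition for entering the prospective phase. Protocol 3.3.2 says what that means. Criterion 2 asks for "Patients with available medical records for data abstraction to meet the objectives of the study". Criterion 9 asks for "At least 4 serum creatinine values in the retrospective phase", with the latest no more than 6 months before Visit 1. On span it says "The most recent and oldest serum creatinine values should be no less than 1 year apart and no greater than 5 years apart". Its fourth condition rules out any interval of 2 years or more without a value.

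SAP 4.5.1 puts disposition on the enrolled set and promises "A breakdown of the number of patients that did not meet each inclusion/exclusion criterion" among screen failures. It also lists each enrolled patient with the reason for not entering.

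The SAP revision history refers to a summary of retrospective period length in section 4.10.3.2. That section is not in the public text.

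**The concern.** Number of values, recency, span and gaps are what one would tabulate to describe availability, frequency and continuity. They are also the variables on which criterion 9 selects. A table restricted to patients who passed the criterion describes records already known to be adequate. The patients whose records fell short, who carry the information on availability, appear only as a count in disposition.

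A reader planning a later trial that screens on retrospective slope could take the FAS tables as describing CKD patients in routine care. Such a reader would expect too few screen failures for inadequate records. Nothing in the visible text says that the FAS figures apply only to patients who met the record rule.

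**Working it through.** The plan gives no figure for record availability, so there is none to reproduce. The precision statements in SAP 4.12 concern the proportion of fast progressors and do not bear on this point.

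**Step 1. Compare what is described with what is selected.**

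| Feature to be described | Condition for entry (criterion 9) | Effect in the FAS |
|---|---|---|
| Availability of eGFR values | At least 4 creatinine values | Share meeting the minimum is 100%, barring deviations |
| Recency | Last value within 6 months of Visit 1 | Cut off at 6 months |
| Span | 1 to 5 years | Cut off at both ends |
| Continuity | No gap of 2 years or longer | Cut off below 2 years |
| Frequency | Only through the minimum of 4 and the span | Partly truncated |
| UACR/PCR availability | None | Not truncated by criterion 9 |

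These conditions are those of protocol version 3.0. Its amendment log shows that the recency and gap rules were added in April 2022 and the span limits changed then. The minimum of 4 values applied throughout. For patients who entered earlier, the cut-offs on recency, gap and span differ.

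**Step 2. Size for availability.** Let q be the true share of consented patients who meet the record rule. The FAS shows 100%, so the excess is 100 × (1 − q) points. The documents give no q. For assumed values of 50%, 70%, 80%, 90% and 95%, the excess is 50, 30, 20, 10 and 5 points. If records were the only reason for failure, reaching 600 eligible patients would take 600/q consented: 1200, 858, 750, 667 and 632.

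**Step 3. Size for frequency.** Assume the number of values X is Poisson with mean m and keep only X ≥ 4. Then E[X | X ≥ 4] = m × P(X ≥ 3) / P(X ≥ 4).

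| True mean m | P(X ≥ 4) | Mean among those kept | Excess |
|---|---|---|---|
| 3 | 0.353 | 4.91 | +1.91 (63.5%) |
| 4 | 0.567 | 5.38 | +1.38 (34.5%) |
| 6 | 0.849 | 6.63 | +0.63 (10.5%) |
| 8 | 0.958 | 8.24 | +0.24 (3.0%) |
| 10 | 0.990 | 10.08 | +0.08 (0.8%) |
| 11 | 0.995 | 11.04 | +0.04 (0.4%) |
| 22 | 1.000 | 22.00 | 0 |

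**Step 4. Where the trial may lie.** Protocol 1.4.2 expects most CKD patients to give venous samples at least every 3 to 6 months. Over the 5.5-year window this is 5.5 × 2 = 11 to 5.5 × 4 = 22 values, where the excess is 0.4% or less. The stated reason for widening the window in Amendment 2 was to admit patients who reach 4 values only over a longer period. Some candidates therefore lie near the top of the table, but the documents do not say how many.

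**The case against.** The strongest objection is that part of the SAP is out of sight. Section 4.10.3.2 exists, the contents list is blacked out after 4.10.2, and so are the objectives after the first. The analysis set for record summaries is inferred from the general sentence in 4.6, and the SAP itself departs from that sentence for disposition. This stands, and the fix is conditional for that reason.

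A reader might infer that every output uses the FAS and that patients with inadequate records disappear from the report. The documents do not support this. SAP 4.5.1 works on the enrolled set, so the number failing criterion 9 as a whole can be read from it. What it does not give is which condition failed, or the counts, gaps and spans behind the failure.

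A reader might also infer that everything said about record availability is overstated by construction. That is too broad. UACR/PCR has no eligibility minimum. Number and spacing of eGFR values still vary above the threshold, and with dense testing the mean count is barely affected. No visible output reports the share of patients with sufficient data, so a figure of 100% is something a reader could derive, not something the plan says it will publish.

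Finally, availability appears in introductory text, while the visible objective and primary outcome concern slope homogeneity. The regulatory advice as described does not ask for the prevalence of adequate records, and the visible text contains no phase III screening forecast. This limits the weight of the point, but both documents still state the aim.

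**Conclusion.** The point holds in a limited form. Under the general rule in SAP 4.6, summaries of eGFR record availability and continuity are conditional on criterion 9 and cannot estimate how often routine records are adequate. For availability this follows from the eligibility rule alone. Its size in percentage points depends on a true rate that the documents do not give (5 to 50 points over the assumed range of 95% to 50%). For the mean number of values, the bias rests on the Poisson assumption and on testing density: material with sparse records, negligible at the testing rate in Protocol 1.4.2.

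The point affects one descriptive aim. It does not touch the primary shift table or UACR/PCR availability. It would narrow to labelling and the split of criterion 9 if 4.10.3.2 already uses the enrolled set.

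**What to change.** Unless section 4.10.3.2 already does so:

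1. Present the retrospective eGFR summaries (number of values, recency, span, longest gap) on the enrolled set as well as the FAS. The flow chart schedules historical creatinine from Visit 1, and Protocol 3.1 asks for all available historical eGFR values for each patient.
2. In the SAP 4.5.1 breakdown, split criterion 9 failures into its four conditions: number, recency, span, gap. Note the protocol version under which each patient was screened.
3. Label FAS versions as conditional on meeting criterion 9.
4. Reword SAP 4.6 so that it agrees with the enrolled-set outputs in 4.5.1.

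The cost is SAP wording, one or two descriptive tables and a footnote.

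There are two limits. Records of screen failures may be incomplete: Protocol 6.2.2 requires failures to be registered in source documents, which does not guarantee full creatinine histories in the database, and the trial ended in July 2022. The number of screen failures with usable histories should be shown. Patients never asked for consent because of poor records also stay unseen. On that account the enrolled-set figures remain an upper bound on availability and should be described so, with the caveat that missing histories among screen failures would pull the other way. A pre-screening log, if one exists, would help.

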#### 4.10.1.2 Handling of Dropouts or Missing Data

Missing data will not be imputed for the primary analysis. Data which will be excluded from the analysis is defined in section 4.10.2.

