#### 4.10.2 Primary Outcome Variable

The primary outcome is the homogeneity (eGFR slope shift table) between eGFR slopes derived from retrospective and prospective eGFR values. All analyses of the primary outcome will be done on the FAS, and percentages will be based on the number of patients in the FAS, unless otherwise specified.

Retrospective and prospective eGFR slopes will be derived using a linear random slope model. The prospective eGFR slope for each patient will be derived using eGFR values in the prospective phase as the dependent variable and time in the prospective phase (years, starting from baseline) as the continuous independent variable with random intercept and random slope. The retrospective eGFR slope for each patient will be derived similarly using the data in the retrospective phase, and time in the retrospective phase will be calculated relative to the first retrospective measurement per patient. Note that for the prospective slope, all measurements from baseline until the last available visit will be considered for inclusion in the estimation, including unscheduled visits.

The primary analysis assessing homogeneity between retrospective and prospective eGFR slopes will first be performed using the retrospective eGFR slopes collected from retrospective data, and the prospective eGFR slopes derived using prospective eGFR measurements from Mitra® samples from both at-home and clinic visits. The primary analysis will then be performed again using the retrospective eGFR slopes collected from retrospective data, and prospective eGFR slopes derived from prospective eGFR measurements from venous blood samples from clinic visits. This is in order to assess differences in the slope estimation depending on the data source.

Other than this requirement, all available patient data will be included for the estimation of the retrospective slope. However, for the prospective slope, the following additional data resulting from changes to background therapy will be excluded from the eGFR slope estimation:

- For patients on SGLT2i/ACEi/ARB background therapy at date of eGFR baseline measurement, eGFR data collected after the patient dropped out of SGLT2i/ACEi/ARB will be excluded
- For patients who are not on SGLT2i/ACEi/ARB background therapy at date of eGFR baseline measurement, eGFR data collected after the patient starts SGLT2i/ACEi/ARB will be excluded

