- For patients who are on ACEi/ARB background therapy at date of eGFR baseline measurement, eGFR data occurring after a change in ACEi/ARB dose occurs will also be excluded.

If the eGFR baseline measurement in the above definition is missing, then the date of study Day 1 will be used, per the definition in section 4.2.

These background therapies will be identified via the following WHO-DD ATC codes:

Therapy Type	ATC Codes
SGLT2i	A10BK
ACEi	C09A, C09B
ARB	C09C, C09D

The linear random slope for the eGFR values  $Y_{ij}$  at time  $i$  for patient  $j$  will be estimated via a linear mixed regression model (using restricted maximum likelihood) with the following model form, assuming the  $Y_{ij}$  follow a Normal distribution

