**Equation 1**

$$E(Y_{ij}) = a_0 + b_{0j} + (a_1 + b_{1j})T_{ij}$$

Where  $a_0$  is the fixed effect term for the common intercept (across all patients),  $b_{0j}$  is the term for the random intercept of patient  $j$  and follows a Normal distribution,  $a_1$  is the fixed effect term for the common slope (across all patients) and  $b_{1j}$  is the term for the random slope of patient  $j$  and follows a Normal distribution.  $T_{ij}$  represents the time (in years) in the phase for patient  $j$  and time  $i$ . For a given patient, the random slope quantifies the difference between the observed eGFR slope of the patient and the population-averaged (common) eGFR slope. Therefore the combination of  $a_1 + b_{1j}$  represents the eGFR slope for each patient, and will be the primary quantity of interest in this analysis. The primary analysis will come from an unadjusted model as shown above. An autoregressive covariance structure will be used in this model in the first instance, however other covariance structures may be used, especially in the case of model non-convergence. If an autoregressive covariance structure results in non-convergence, then a compound symmetry structure will be tried. In the case that neither of these covariance structures results in convergence, other structures may be tried and the final choice of covariance structure will be detailed in the output. Note that the eGFR slope resulting from Equation 1 is expected to be negative as eGFR is expected to decline over time.

[figure not shown]
The primary analysis used to evaluate homogeneity of the slopes will be a shift table of the shift in number of patients with categories of estimated eGFR slopes of  $> -1$ ,  $> -3$  to  $-1$  (slow progression) and  $\leq -3$  mL/min/1.73m^2/year (fast progression) from the retrospective phase to the prospective phase. This analysis will be presented overall and for the DKD and non-DKD populations. Percentages will be based on the number of patients within each category in the retrospective phase. This analysis will

[figure not shown]
be performed once using prospective eGFR measurements from Mitra® samples and once using prospective eGFR measurements from venous blood samples.

[figure not shown]

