#### 4.12 Determination of Sample Size

The trial is initially planned to be conducted in a cohort of 600 patients, pending feasibility and enrolment period. To obtain a good representation of patients across eGFR slopes spectrum, 600 patients are planned to be enrolled. The goal is to achieve 400 fast progressors with an eGFR slope  $\leq -3$  ml/min/1.73m^2/year and 200 slow progressor patients with an eGFR slope between  $-3$  and  $-1$  ml/min/1.73m^2/year).

The sample size determination is not based on statistical considerations, but on feasibility, and there is no formal statistical hypothesis defined in the study. However, the sample size of 600 patients is considered adequate to evaluate the homogeneity of the retro- and prospective slopes. If the true (unobserved) proportion of patients have an eGFR slope  $\leq -3$  mL/min/1.73m^2 based on retrospective data and in the prospective observed period is 70%, 600 patients will provide an estimate of the proportion of at least 67% with a probability of 95%.

On the other hand, if the true (unobserved) proportion of patients have an eGFR slope  $\leq -3$  mL/min/1.73m^2 based on retrospective data and in the prospective the observed period is 50%, 600 patients will provide an estimate of the proportion of at least 47% with a probability of 95%. Results based on these parameters would be considered less than success, i.e. that we are less likely to be able to suggest or “conclude” that the retrospective and prospective slopes are homogeneous.

This study was terminated in July 2022, due to decision of the sponsor (see section 3.1.1.1). All enrolled patients and their data available up to the termination will be used in any subsequent analyses.

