#### 4.13 Changes in the Conduct of the Study or Planned Analysis

The presentation of eGFR slope categories in this SAP differs from that of the protocol (e.g. the protocol specifies eGFR slope category ‘<1’ but this SAP specifies ‘>-1’) because the wording in this SAP reflects the value of the eGFR slope coming directly from the statistical mixed model, whereas the protocol refers to the eGFR decline rate that is equal to the negative value of the eGFR slope coming from the statistical model.

For the primary analysis, an additional eGFR slope category ‘> -1’ for the shift table will be presented in order to assess homogeneity of eGFR slopes for patients with an eGFR slope of  $> -1$ . The analysis specified in the CTP will be modified to a shift table of patients with categories of eGFR slopes of  $> -1$ ,  $> -3$  to  $-1$  and  $\leq -3$  mL/min/1.73m^2/year in each of the retrospective and prospective phases.

Summaries of clinically relevant laboratory abnormalities will not be performed as per the CTP due to a lack of available data.

As detailed in section 3.1.1.1, this study was terminated in July 2022.

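### The readable shift-table rule sets no minimum prospective follow-up, so a patient with about 12 weeks or less is classified mainly by the cohort mean or by noise, not by their own slope

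*SAP*

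**What the plan says.** SAP 4.6 defines the FAS as "all patients entered into the 48-week prospective phase of the study who have at least one post-baseline assessment". The assessment may be of any kind and need not be an eGFR value.

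SAP 4.10.2 runs the primary outcome on the FAS. For the prospective slope, "all measurements from baseline until the last available visit will be considered for inclusion in the estimation". Values are then removed after stated changes in background therapy; for example, "eGFR data occurring after a change in ACEi/ARB dose occurs will also be excluded". No amount of data has to remain after these cuts.

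Each patient's slope is the common slope plus that patient's predicted random slope (Equation 1). It is placed in one of three categories: above −1, above −3 to −1, or −3 and below. The table is shown overall, by DKD and non-DKD, and by Mitra and venous source. "Percentages will be based on the number of patients within each category in the retrospective phase". The model uses an autoregressive covariance structure first and compound symmetry if that fails. The text does not say whether the structure applies to the residuals or to the random effects.

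On the termination, SAP 3.1.1.1 says "All data available up to the termination will be used in any subsequent analyses and all analyses planned in this SAP" will be carried out. SAP 4.12 adds: "All enrolled patients and their data available up to the termination will be used in any subsequent analyses". SAP 4.13 only records the fact: "As detailed in section 3.1.1.1, this study was terminated in July 2022".

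**The concern.** The table was designed for 48 weeks of prospective sampling but will be run on whatever follow-up existed when the study stopped. A slope over a few weeks carries very little information about the patient, yet it produces a category that counts as much in the row percentages as a completer's.

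Those row percentages are the primary evidence on homogeneity. If a noticeable share of patients had short follow-up, part of the apparent agreement or disagreement between phases would come from the estimation method. A reader of the FAS table alone could not separate the two.

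**Working it through.** **The plan's own figure.** The only quantitative design statement is in SAP 4.12: with 600 patients, an estimate of at least 67% (true 70%) or at least 47% (true 50%) with probability 95%. Exact binomial tails give 0.949 and 0.935, so it reproduces to within 2 points. It says nothing about follow-up.

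**Inputs from the documents.** Mitra samples at weeks 0, 2, …, 12, then every 4 weeks to week 48; venous samples at weeks 0, 12, 24, 36 and 48 (SAP 3.1). Category cuts at −1 and −3 (SAP 4.10.2).

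**Assumed, because the documents give no values.** Between-patient slope SD 2–3 and residual SD 3–5 (ml/min/1.73m², slope per year), intercept SD 15, independent random effects and residuals.

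**Slope reliability.** R = σ_b² / (σ_b² + σ²/Sxx), where Sxx = Σ(t − mean t)² and t is in years. For venous data at 12 weeks, t = 0 and 0.230, so Sxx = 0.230²/2 = 0.0264. The lowest R is 4/(4 + 25/0.0264) = 0.004 and the highest is 9/(9 + 9/0.0264) = 0.026. The same formula gives:

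| Weeks | Mitra: values, Sxx | Mitra R | Venous: values, Sxx | Venous R |
|---|---|---|---|---|
| 12 | 7, 0.0411 | 0.007–0.04 | 2, 0.0264 | 0.004–0.026 |
| 24 | 10, 0.2041 | 0.03–0.17 | 3, 0.1058 | 0.02–0.10 |
| 36 | 13, 0.6186 | 0.09–0.38 | 4, 0.2645 | 0.04–0.21 |
| 48 | 16, 1.3714 | 0.18–0.58 | 5, 0.5289 | 0.08–0.35 |

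With wider assumptions (slope SD 2–5, residual SD 3–6), R at 12 weeks is still at most about 0.10.

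**Which category a 12-week patient gets.** This depends on the covariance placement.

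- *Slope variance estimated freely.* The predicted slopes have SD of about σ_b√R. For Mitra with slope SD 3 and residual SD 3, that is 3 × √0.0395 = 0.60. At a cohort mean of −3.5, the share classed fast is Φ(0.5/0.60) = 80%. Over the assumed range it is 80–100% (Mitra) or 85–100% (venous). At a mean of −2.5 it is 0–20% or 0–15%. At −3.0 it is 50%, because the mean sits on the cut.
- *Autoregressive structure on the 2×2 random-effects matrix.* Intercept and slope then share one variance. REML simulations (300 patients, one third each with 12, 24 and 48 weeks, 8 replicates, slope SD 3, residual SD 4) estimated it at about 150–170, against a true slope variance of 9. The 12-week predicted slopes had SD 5.5–6.0. Only 53–55% fell in the cohort-mean category at mean −4, and 14–15% at mean −2.2. A closed-form check with shared variance 117–150 gives SD 3.6–6.2 and 53–56% classed fast at mean −3.5.

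**Effect on the table, slope variance free.** Change per 10% of the FAS = 0.10 × (mean share classed fast at 4, 8 and 12 weeks − mean share at 24, 36 and 48 weeks). In absolute points this is:

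| Cohort mean | Mitra | Venous |
|---|---|---|
| −3.0 | 0 | 0 |
| −2.5 or −3.5 | 1.9–3.0 | 1.1–2.8 |
| −5.0 | 0.03–1.3 | 0.0–0.7 |

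A simulation gave each patient the same true slope in both phases, with an assumed retrospective record of 6 values over 3 years or 10 over 4. The largest change in a row percentage per 10% affected was 4.9 points (Mitra) or 4.2 (venous). Even with a full 48 weeks, at mean −3.5, 41–63% (Mitra) or 50–77% (venous) of retrospectively slow patients were classed fast.

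**Dates.** Assume data stopped by 31 July 2022. Anyone first screened under protocol 3.0 (25 April 2022) then had at most 97 days, or 13.9 weeks. A full 48 weeks (336 days) needs a baseline visit by 29 August 2021, which is 20.7 weeks after the original protocol date of 6 April 2021. If data instead ran to the SAP 2.0 date, 17 October 2022, the 97 days become 175 days (25.0 weeks).

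**The case against.** A reader might infer that short-follow-up patients would mostly fall into the cohort-mean category. The SAP does not support that as a general statement. It holds only if the slope variance is estimated freely and the mean is not close to a cut. With the autoregressive or compound symmetry structure on the random effects, the slopes scatter instead. This objection stands, and it limits the point to a category that is not driven by the patient's own slope.

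The effect may also be small or absent. The overall shift is nil at a mean of −3.0 and can be close to nil at −5.0. The dates show what was possible, not that any patient had short follow-up. This stands as a limit on size.

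Follow-up length is not the only weakness, because slopes are unreliable even at 48 weeks. This also stands. A 24-week minimum would not cure the problem, since reliability there is 0.02–0.17.

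A reader might also infer that the plan has no rule at all. That cannot be established. SAP 4.10.1.2 says "Data which will be excluded from the analysis is defined in section 4.10.2", but the exclusion around acute kidney injury that 4.10.2 mentions cannot be read in full. Sections 4.10.2.2 and 4.10.3 are not readable, and the Protocol Deviation Specification is a separate document.

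Finally, the SAP plans by-patient eGFR listings, disposition counts, residual variance and a possible analysis-set meeting, and the protocol (7.2.2) plans a continuous association analysis. These would let someone reconstruct follow-up. None of them, as described, shows shifts by follow-up, and the meeting has no stated follow-up criterion.

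**Conclusion.** The point holds in limited form and is worth fixing. In the readable SAP, the primary table includes every FAS patient whatever the amount of prospective eGFR data, with no breakdown by follow-up, and the known termination leaves this unchanged. With about 12 weeks or less of usable values, the category comes from the cohort mean or from noise.

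The size rests on assumed SDs and independent effects. The number of short-follow-up patients and the cohort mean are not in the documents, so the effect on the actual table cannot be stated. It would be wrong to conclude that the table is invalid or that patients should be dropped. The study is exploratory, and keeping the whole FAS is defensible.

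**What to change.** Keep the FAS shift table and the model fit unchanged. Add to SAP 4.10.2:

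> For each prospective source (Mitra, venous), the number of patients by span from first to last usable eGFR value (<12, 12 to <24, 24 to <36 and ≥36 weeks, allowing for visit windows) is reported. The three-category shift table is repeated by these bands, with the ≥36-week table as the pre-specified sensitivity analysis. In these added tables, patients with fewer than two usable values from that source are shown as not evaluable. The report states whether the row percentages differ materially from the FAS table, and that slopes remain strongly shrunk or noisy even at 48 weeks.

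To allow for the ±4-day window counted from Day 1, the bands can be cut at 84 − 4 − 1 = 79, 168 − 4 − 1 = 163 and 252 − 4 − 1 = 247 days.

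Also state whether the autoregressive structure applies to the residuals or to the random effects. If a minimum or a breakdown already exists elsewhere, cite it in 4.10.2.

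The cost is a paragraph of text, one span variable per source and a few repeat tables from data already collected. The drawbacks are sparse bands and some selection, because discontinuation and therapy changes also shorten follow-up. For that reason the FAS table stays primary.
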